#### Statistical analysis

The primary outcome data (SF-MPQ-2 total score) will be analysed using an ANCOVA model, conditioning on the baseline value of the outcome, in a linear mixed model with restricted maximum likelihood and Satterthwaite degrees of freedom. This model is one of the principled approaches to dealing with missing outcome data under a plausible missing at random assumption; provided a participant has outcome data for at least one of the two timepoints then they will be included in the analysis. We do not plan to conduct any missing-not-at-random sensitivity analysis via multiple imputation, as there is no strong argument to suggest that participants lost to follow up would have fared worse with respect to the primary outcome. Diverse reasons for loss to follow up may include withdrawal on safety grounds (inability to feel the stimulation), unrelated adverse events, adverse device effects (or perception thereof), lack of motivation, competing caring or time constraints, treatment burden, complexity of device set up, and impact of unrelated medical issues. Given the nature of this trial, we do not anticipate missing baseline data but will apply a suitable approach if so. Fixed effects will be time (3 weeks and 3 months), treatment group, and the time-by-treatment interaction, adjusting for baseline SF-MPQ-2. Alongside the fixed effect for baseline, we shall include a baseline-by-time interaction, to allow for a different association between baseline and outcome at each timepoint. To preserve the desired Type 1 error control, an indicator variable (fixed factor) for membership of the four strata defined by the two, two-level stratification factors will be included in the model. We specify the most general and flexible 'unstructured' residual correlation matrix accounting for the repeated measurements nested within participant, imposing no constraints and estimating a variance for each timepoint and their covariance. Therefore, the random participant intercept is omitted ('noconstant'). The primary endpoint will be the estimate of the effect of the intervention at 3 weeks. We shall present the point estimate together with 95% confidence interval and P-value, via t-based inferences using Satterthwaite degrees of freedom. All analyses will be conducted using Stata software (current version: (StataCorp, 2025. Stata Statistical Software: Release 19, College Station, TX, USA: StataCorp LP). Sample draft Stata code for this primary analysis is provided below:

```
mixed sfmpq2 i.group##i.time c.baseline##i.time i.indicator || id: noconstant residuals(unstructured, t(time)) reml  
dfmethod(satterthwaite)
```

The behaviour of the model residuals will be inspected visually using residuals plots, with data transformations applied if indicated. An intention-to-treat analysis (primary; participant included if they have outcome data for at least one of the two timepoints) and a per-protocol analysis (secondary) will be undertaken. In the per-protocol analysis the participant will be required to have undertaken at least 10 sessions of sensory discrimination training totalling (600 minutes) to be considered suitable for inclusion in the analysis. The primary analysis will be carried out by a statistician blinded to group assignment.

The three secondary outcome measures will be treated as continuous and analysed in the same way, but obviously with no baseline value for the General Subjective Outcome Score (GSOS). The secondary outcomes are considered equally important, after a significant primary. Type I error for the analysis of the secondary outcomes will be

preserved using the Holm multiple testing algorithm. Study diary data will be summarised using descriptive statistics.

**Secondary analysis:** Secondary analysis (non-blinded) will be carried out to explore treatment heterogeneity. By inclusion of appropriate interactions with treatment group, we will explore putative effect modifiers, including baseline value of outcome, age, sex, total treatment time (minutes) with the device, chronicity, and whether the amputation was due to trauma or planned surgery. The trial is not powered for quantifying treatment heterogeneity, so we emphasise that this secondary analysis will be purely exploratory/ descriptive.

**Qualitative analysis:** A purposive sample of participants from the active intervention group will be invited to undergo a semi-structured interview. During these interviews, participants will be asked about the usability and acceptability of the SP1X device. The interviews will be audio recorded, transcribed verbatim, and analysed thematically. Thematic analysis will be undertaken by the research assistant (RA) using the method of Braun and Clarke.

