### **Intervention**

There will be two parallel groups, an intervention group (SP1X) and a placebo group (SP1X7). Both the intervention and placebo device will be provided to participants for use in their own homes. During an online video call the participant will be instructed how to set up and use the device by the RA (an HCPC registered Physiotherapist). The RA will observe the first full treatment session (60 minutes) and up to 30 minutes of the second treatment, and provide any additional advice needed. Participants in both groups will be asked to use the device for 60 min/day, as one block, or as multiple shorter sessions of ≥20 minutes duration on at least 15 days of the 21-day treatment period. They will be asked to spread out the use of the device, over the treatment period and to record their device use in a study diary (figure 1).

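### Is the per-protocol rule of 10 sessions and 600 minutes unworkable when sessions may be as short as 20 minutes and one arm uses a placebo device?

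*SAP*

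**What the plan says.** The Statistical analysis section of the SAP names an intention-to-treat analysis as primary and a per-protocol analysis as secondary. For the latter a participant must have had "at least 10 sessions of sensory discrimination training totalling (600 minutes) to be considered suitable for inclusion in the analysis".

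The Intervention section sets the regimen: "60 min/day, as one block, or as multiple shorter sessions of ≥20 minutes duration on at least 15 days of the 21-day treatment period". It also describes the supervised start: "The RA will observe the first full treatment session (60 minutes) and up to 30 minutes of the second treatment". Session is thus used there both for a full hour and for a shorter part of one.

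On who follows the regimen the section is explicit: "Participants in both groups will be asked to use the device for 60 min/day". Participants are also asked to "record their device use in a study diary", which is the source for counting sittings and minutes.

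**The concern.** Ten sessions make 600 minutes only if each lasts 60 minutes. Someone who takes the hour as three sittings of 20 minutes reaches ten sittings on the fourth day, with 200 minutes of use. Someone who takes the hour in one block and stops after eight days has 480 minutes but only eight sessions. If the count alone decided, the lighter user would enter the per-protocol set and the heavier user would not. The SAP does not spell out whether the count, the minutes or both decide.

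The rule also speaks of sensory discrimination training, a term that appears nowhere else in the SAP and is not defined there, while one arm uses a placebo device. Taken very literally, placebo participants might never qualify, or the adherence filter might be applied to the active arm alone. Either would spoil the comparison, the second by setting selected active users against all placebo participants.

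Membership of an analysis set should not depend on a reading chosen after the data are seen.

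**Working it through.** **Inputs.** From Statistical analysis: at least 10 sessions, 600 minutes. From Intervention: 60 minutes a day, in one block or in sittings of at least 20 minutes, on at least 15 of 21 days, in both groups.

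**1. The plan's own figure.** 10 × 60 = 600 minutes. It reproduces when a session is the full hour, which is how the Intervention section describes the first supervised session.

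**2. The total is a minimum.** Full requested use is at least 15 × 60 = 900 minutes. A full adherer must qualify, so 600 cannot be an exact total. It is a floor, at 600 / 900 = 67% of requested use.

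**3. Count and minutes at the permitted lengths.**

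| Length of each sitting | Minutes in 10 sittings | Sittings needed for 600 minutes |
|---|---|---|
| 20 min | 200 | 30 |
| 30 min | 300 | 20 |
| 40 min | 400 | 15 |
| 60 min | 600 | 10 |

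**4. What the joint rule selects.** Let a participant have k sittings of lengths L₁, …, Lₖ, each at most 60 minutes. Total use is T = ΣLᵢ ≤ 60k. If T ≥ 600, then k ≥ 600 / 60 = 10. Meeting the minutes therefore guarantees meeting the count, and the joint rule is the same as T ≥ 600. Rewriting it in minutes alone moves nobody in or out.

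**5. The two troubling cases.** Ten sittings of 20 minutes give 200 minutes: out. Eight blocks of 60 minutes give 480 minutes: out. The joint rule treats both alike. They separate only if the 600 minutes written in the rule is ignored.

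**6. Where readings could still part.**
- Sittings longer than an hour: 8 × 75 = 600 minutes meets the minutes but not the count. This exceeds the 60 minutes a day requested.
- Part-days: 40 minutes on 15 days is 15 × 40 = 600 minutes in at least 15 sittings. This qualifies under the joint rule and fails only if every session must be a full hour, which the rule does not say.

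**7. The arm question, passages side by side.** The rule refers to the participant and names no arm. The Intervention section gives both groups the same instructions, supervision and diary. No passage reserves sensory discrimination training for the active device, and none describes a filter on one arm.

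**8. Selection bias, as a separate matter.** A simulation took zero device effect, SD 2.13, baseline correlation 0.7, 40 per arm, ANCOVA and the 70% heaviest users kept in each arm. If use is assumed to correlate 0.3 with better outcome in the active arm and 0 in placebo, the spurious benefit is about 0.22 units and the test rejects in about 8.6% of trials. With equal correlations in both arms the bias is 0.00 and rejection is between 5% and 6%. The bias comes from the assumed inequality between arms. It would be the same under a rule in minutes alone, so it does not measure any fault in the wording.

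**The case for a change.** The strongest case is that a reader should not have to deduce which reading applies. The Intervention section itself calls a 20-minute sitting a session, the phrase at least is attached to the count and not to the minutes, and the SAP promises a blinded statistician for the primary analysis without saying that per-protocol membership is settled before unblinding. A choice between readings could then be made with allocation known. A filter on the active arm alone would do harm: with a use–outcome correlation of 0.3 in both arms and no device effect, it gives a spurious benefit of about 0.2 units and rejection in about 9% of trials.

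The looseness of the word stands, and so does the absence of a statement on when membership is settled. The rest has little force. The count-only reading discards a figure that the rule states. The remaining readings agree for anyone whose sittings are full hours, and the joint reading equals the minutes for anyone who stays within the requested hour, so there is little left to choose between. The one-arm filter would be harmful if used, but nothing in the SAP points to it. What the training or the placebo device consists of is commonly left to the protocol, which is not at hand.

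**Conclusion.** No change to the plan follows. The wording is loose, but the rule is coherent: read as written, with count and total together, it means at least 600 minutes of device use, two thirds of the 900 minutes requested, in either arm. An analyst with the diary data would apply it that way, and restating it in minutes would give the same set.

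This rests on two assumptions: that no sitting exceeds 60 minutes, in line with the requested regimen, and that the rule covers both arms, as the common instructions imply. The SAP gives no distribution of sitting lengths, so the number of participants who might depart from the first assumption cannot be stated. Even then the effect would be confined to the per-protocol analysis, which is secondary. The intention-to-treat estimate at 3 weeks, the sample size of 40 per arm after losses, and the Holm procedure for the secondary outcomes do not use this rule. Total device minutes are also examined directly, as an exploratory effect modifier.

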### Exploratory Outcomes

No inferences will be drawn from these outcomes.

- SF-MPQ-2 total score at the 3-month time point.
- TAPES (modified)
- Quality of life [EQ-5D-5L]
- Sleep Disturbance [the PROMIS Short Form v.1.0 – Sleep Disturbance 4a questionnaire]
- Participant satisfaction
- Device Usability [an adapted version of the 10 question System Usability Scale (SUS)].
- Study Diary of device and medication usage
- Concordance with Protocol
- Success of blinding

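### Total device time builds up after randomisation, so its interaction with treatment group cannot by itself tell a dose-response from selection

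*SAP*

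**What the plan says.** The Secondary analysis paragraph under Statistical analysis plans to study treatment heterogeneity by adding interactions with group: "we will explore putative effect modifiers, including baseline value of outcome, age, sex, total treatment time (minutes) with the device, chronicity". Cause of amputation (trauma or planned surgery) completes the list of six.

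The Intervention section shows when and where device time arises. "Participants in both groups will be asked to use the device for 60 min/day", "on at least 15 days of the 21-day treatment period", and they are asked "to record their device use in a study diary".

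Three statements limit how such results may be read:

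- On the heterogeneity analysis: "The trial is not powered for quantifying treatment heterogeneity, so we emphasise that this secondary analysis will be purely exploratory/ descriptive".
- On the diary: "Study diary data will be summarised using descriptive statistics".
- Under Exploratory Outcomes, "No inferences will be drawn from these outcomes" heads a list that includes "Study Diary of device and medication usage".

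**The concern.** For baseline score, age, sex, chronicity and cause of amputation, randomisation makes the arms comparable at every level of the modifier. An interaction with group is then a contrast of randomised comparisons, however imprecise.

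Device minutes differ in kind. They are determined after allocation, and the allocated device and the course of the pain may both affect them. An active and a placebo participant who each logged the same minutes may have reached that total for different reasons. The SAP's own reasons for loss to follow-up include not feeling the stimulation, perceived device effects and lack of motivation. These could plausibly also shorten use, and some could act differently in the two arms. That is an inference; the SAP does not say it.

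For a home-use device, a positive group-by-minutes interaction invites the reading that more use brings more benefit. Listing minutes among baseline characteristics encourages that reading, although selection that differs by arm could produce the same pattern.

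**Working it through.** The point rests on the timing of a variable, so no formula decides it. The arithmetic below shows what the interaction would estimate under stated assumptions.

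**Inputs from the SAP (Sample size section).** Target difference 1 unit, SD 2.13, baseline-outcome correlation 0.7, 40 analysed per arm, two-sided 0.05.

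**The SAP's own figure.** The residual SD after baseline adjustment is 2.13 × √(1 − 0.7²) = 1.521. The standard error of the group difference is 1.521 × √(2/40) = 0.340. Power is Φ(1/0.340 − 1.96) = 83.6%, which agrees with the stated c.84%.

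**Assumptions, none from the SAP.** Minutes are centred and scaled in active-arm SD units. Within arm g, minutes have SD s_g (s_A = 1) and correlate ρ_g with a better (lower) baseline-adjusted outcome, without causing it. The treatment benefit is a constant 1 unit.

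**What the interaction picks up.** In arm g, regressing outcome on minutes gives a slope of −ρ_g × 1.521 / s_g. The apparent benefit at minutes m is therefore

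benefit(m) = 1 + m × 1.521 × (ρ_A/s_A − ρ_P/s_P).

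- ρ = 0.3/0.3, equal spread: the slopes cancel and the benefit is 1 everywhere.
- ρ = 0.3/0: 1.521 × 0.3 = 0.456, so 0.54 at −1 SD and 1.46 at +1 SD.
- ρ = 0.3/0.3, placebo spread halved: 1.521 × (0.3 − 0.6) = −0.456, so the pattern reverses.

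**Simulation.** There were 20,000 trials per scenario. Each was analysed by least squares on baseline, group, minutes, group × minutes and a four-level stratum indicator, with a t-test on 72 df. Monte Carlo standard error is at most 0.3 points.

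| Scenario (active / placebo) | Interaction CI excludes 0 | Apparent benefit at −1 SD / +1 SD |
|---|---|---|
| Selection 0.3 / 0.3, equal spread | 4.9% | 1.00 / 1.00 |
| Selection 0.3 / 0.15 | 9.8% | 0.77 / 1.23 |
| Selection 0.3 / 0 | 25.4% | 0.54 / 1.46 |
| True active-arm dose effect of 0.456 per SD, no selection | 25.2% | 0.55 / 1.46 |
| Same dose effect, selection 0 / 0.3 | 4.9% | 1.00 / 1.00 |
| Selection 0.3 / 0.3, placebo spread half of active | 13.2% | 1.46 / 0.55 |

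**Hand check of the third row.** The residual variances given minutes are 1.521² × 0.91 = 2.11 and 1.521² = 2.31. The standard error of the interaction is about √((2.11 + 2.31)/37) = 0.346, taking 37 = 40 − 3 for the expected inverse sum of squares. Then 0.456/0.346 = 1.32, and Φ(1.32 − 1.99) is about 25%.

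**Closer to the SAP's model.** Both timepoints were fitted with an unstructured residual covariance, an assumed residual correlation of 0.6 and complete data, using 73 df rather than Satterthwaite (3,000 trials). The 3-week interaction gave 5.3% (0.3/0.3), 9.7% (0.3/0.15), 26.5% (0.3/0) and 25.2% (true dose effect).

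The third and fourth rows carry the point: pure selection and a real dose-response give the same picture. The fifth row shows that a real dose effect can also be hidden.

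**The case against.** The strongest reply is that the placebo arm also has minutes, collected under the same instructions. Selection common to both arms cancels, as the first row shows, and nothing in the SAP demonstrates that selection differs by arm. This stands as far as it goes: differential selection is assumed here and its size is unknown. It does not rescue the interaction as a dose-response analysis, because the trial data cannot show whether selection matches. Equal correlations are also not enough if the spread of minutes differs.

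The match between the third and fourth rows is built in, since the dose effect was set equal to the selection slope. That is fair as a criticism of any attempt to estimate the size. The rows are there only to show that the two explanations can yield the same result. In the halved-spread row, ±1 active SD is ±2 placebo SD, so that reading leans on the extremes of the placebo data.

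The SAP already calls the analysis exploratory and descriptive. The reason it gives is low power, which warns of imprecision; a larger sample would not remove selection. The no-inference statement covers the listed exploratory outcomes and does not mention this interaction.

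Finally, no decision depends on this term, and the SAP sets no significance threshold for it. The percentages only gauge how often a pattern would look convincing. This also stands, and it keeps the point minor.

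**Conclusion.** The concern holds. Device minutes are a post-randomisation variable placed in a list of baseline effect modifiers. Their interaction with group identifies a dose-response only under an unstated assumption of equal selection and equal spread across arms.

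The size cannot be estimated from the SAP. Under the assumed correlations, the rate of nominally significant interactions with no true interaction runs from about 5% (no bias) to about 25%, and the apparent trend can go in either direction. The consequence is limited to how one exploratory result is read. The primary estimate, its power and the Holm-controlled secondary tests are untouched, so this is a cheap, optional improvement.

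**What to change.** Limit the effect-modifier list to variables measured before randomisation: baseline score, age, sex, chronicity and cause of amputation. Report device minutes by arm within the diary summary already planned.

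If a group-by-minutes term or a use-outcome association is still wanted, report it apart from the effect-modifier analysis with a sentence such as: *Device time is measured after randomisation; this is a non-randomised association that cannot be separated from selection.*

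The cost is a change of SAP wording. No new data are needed, and the sample size and the primary and Holm-controlled analyses stay as they are. What is given up is presenting the device-use interaction as effect modification; the result itself can still be shown under its own label.

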### **Sample size**

We regard the maximum feasible sample size within the constraints of this trial as a total of 100 participants. With an estimated loss to follow-up of 20%, the effective sample size is 80 participants (40 per group in a 1:1 allocation ratio). Our targeted effect size is a difference in follow-up (3-week timepoint) SF-MPQ-2 total score between arms of 1 unit – a moderate clinically relevant effect size. The between-subjects variability (SD) was derived from a small reliability study with 37 participants drawn from the same population as the proposed trial (unpublished observations). The observed SD was 2.13 units. The pre-post correlation (with one week between test and retest) was 0.82. The pre-post correlation (the reliability of the measure) is expected to decrease over time. Estimates for the decline in correlation with more distant pairs of timepoints post-randomisation range from -0.003 per month to -0.009 per month. We have assumed a conservative value for this correlation of  $r=0.7$  at the 3-week primary endpoint. An effective sample size of 40 participants per arm gives c.84% power at 2-sided  $P=0.05$  to detect the targeted effect size. This sample size estimate was derived assuming an ANCOVA analysis model, adjusting for the baseline value of the outcome measure. To allow reproducibility of our sample size estimate, the relevant Stata code is provided herein (StataCorp, 2023. Stata Statistical Software: Release 18, College Station, TX, USA: StataCorp LP): *sampsiz 5 4, sd1(2.13) sd2(2.13) method(ancova) pre(1) post(1) r01(0.7) n(40) n2(40)*.

### **Randomisation**

The RA will use the Sealed Envelope™ remote randomisation software system to randomise participants (1:1) to one of two trial groups: 1) Intervention Group (SP1X) 2) Placebo Group (SP1X7). A unique participant identification code (e.g., 001, 002) will be allocated to all participants. The allocation will be stratified by sex (male/ female) and chronicity (<6 months/ ≥6 months post-surgery), generating four separate strata. Within these strata, participants will be allocated using a mixed (unrestricted and restricted) randomisation approach. This approach uses an initial simple (unrestricted) randomisation to provide unpredictability and guard against guessing followed by allocation using randomly permuted blocks to achieve reasonable balance, resulting in approximately 50 participants per arm overall. More explicit details of the randomisation scheme are not provided herein, to avoid the facilitation of the deciphering of the allocation sequence.

